### 3. DESCRIPTION OF DESIGN AND TRIAL POPULATION

#### 3.1 OVERALL TRIAL DESIGN AND PLAN

This is an open-label trial of BI 695501 with a 48-week treatment period in patients with RA continuing to receive MTX within the dose range of the 1297.2 trial for at least 12 weeks. After Week 12, the MTX dose will be at the Investigator's discretion.

The trial will consist of a Screening visit 14 days prior to Day 1, a 48-week treatment period and a 10-week safety follow-up visit. The Screening visit will be the Week 48 visit in Trial 1297.2. Informed consent for this extension trial must be obtained prior to conducting the Week 48 assessments in Trial 1297.2, in order for those assessments to serve as the screening assessments in this extension trial. Trial medication should be administered after completion of all assessments at the Screening visit; this will be the last administration of trial medication in Trial 1297.2.

Patients who discontinue the trial medication early (and do not withdraw consent) should return to the site for an End of Treatment (EoT) visit equivalent to the Week 48 assessments as soon as possible after last trial medication administration. For patients who discontinue treatment early, a safety follow-up visit should be performed 10 weeks after the last administration of BI 695501. All patients who complete the trial should return for a safety follow-up visit at Week 58.

It is anticipated that approximately 300 to 400 patients with moderately to severely active RA who have completed Trial 1297.2 will be eligible and willing to participate in this extension trial. Each patient who provides informed consent and meets all the inclusion criteria and none of the exclusion criteria will self-administer 40 mg of BI 695501 every 2 weeks by SC injection.

Patients will undergo up to 10 visits over the duration of the trial (58 weeks). The trial procedures to be undertaken at each visit are shown in the [Flow Chart](#).

The primary endpoint of this trial is defined as the number (proportion) of patients with drug-related AEs during the treatment phase. Efficacy and other safety parameters will be assessed as secondary and other endpoints. For more details, see [Section 5.1](#).

Up to Week 12, patients will continue to take their regular MTX therapy and the associated stable weekly dose of adequate folic acid (at least 5 mg per week or as per local practice) or folinic acid (at least 1 mg per week or as per local practice) from their usual source. After Week 12, MTX therapy may be adjusted based on Investigator assessment. Patients may also continue to receive treatment with oral corticosteroids at a dose of  $\leq 10$  mg/day prednisolone or equivalent.

Patients may return for unscheduled visits should their medical condition warrant urgent attention at the discretion of the Investigator.

The trial is designed to generate data on long-term safety, efficacy, PK, and immunogenicity with BI 695501 in patients who have completed Trial 1297.2. This will include:

- patients who were previously treated with BI 695501 in Trial 1297.2 for 48 weeks,
- patients who were previously treated with US-licensed Humira® for 24 weeks followed by BI 695501 for 24 weeks in Trial 1297.2, and
- patients who were previously treated with US-licensed Humira® in Trial 1297.2 for 48 weeks.

### **3.1.1 Administrative structure of the trial**

will perform Project Management, Clinical Field Monitoring, Medical Monitoring, Data Management and Statistical Evaluation according to Standard Operating Procedures. A list of responsible persons and relevant local information can be found in the ISF.

A Coordinating Investigator will be nominated and will be responsible to coordinate Investigators at different centers participating in this multicenter trial. Tasks and responsibilities will be defined in a contract. Relevant documentation on the participating (Principal) Investigators and other important participants, including their curricula vitae, will be filed in the electronic trial master file.

### **3.2 DISCUSSION OF TRIAL DESIGN, INCLUDING THE CHOICE OF CONTROL GROUP(S)**

This is a long-term, open-label extension trial to assess the safety, efficacy, PK, and immunogenicity of BI 695501 in patients with RA who have completed Trial 1297.2 and are eligible for long-term treatment with adalimumab. The trial has a 48-week treatment period in patients with RA continuing to receive MTX within the dose range of the 1297.2 trial for at least 12 weeks. After Week 12, the MTX dose will be at the Investigator's discretion. All patients will be treated with BI 695501. No comparator was chosen as the purpose of the trial is to collect data on the long-term safety (and efficacy) and to better characterize PK and immunogenicity of BI 695501.

Each patient who meets all the inclusion criteria and none of the exclusion criteria will self-administer 40 mg of BI 695501 every 2 weeks. This is the same dosing regimen the patients received in Trial 1297.2.

### **3.3 SELECTION OF TRIAL POPULATION**

A log of all patients enrolled into the trial (i.e., who have signed informed consent) will be maintained in the ISF at the investigational site irrespective of whether they have been treated with investigational drug or not.

### **3.3.1 Main diagnosis for trial entry**

The main requirements for trial entry include patients who completed Trial 1297.2, wish to participate in this extension trial, and in the Investigator's assessment can benefit from receiving BI 695501.

Please refer to [Section 8.3.1](#) (Source Documents) for the documentation requirements pertaining to the inclusion and exclusion criteria.

### **3.3.2 Inclusion criteria**

1. All patients must sign and date an Informed Consent Form consistent with ICH GCP guidelines and local legislation prior to participation in the trial (i.e., prior to any trial procedures, which include medication washout and restrictions) and be willing to follow the protocol.
2. Adult patients with moderately to severely active RA who have completed Trial 1297.2, and who wish to participate in this extension trial and in the Investigator's assessment can benefit from receiving BI 695501.
3. Patients willing and able to self-administer BI 695501 pre-filled syringe.
4. For participants of reproductive potential (males and females), a reliable means of contraception has to be used throughout trial participation. Acceptable methods of birth control include, for example, birth control pills, intrauterine devices, surgical sterilization, vasectomized partner and double barrier method (for example male condom in combination with female diaphragm/cervical cap plus spermicidal foam/gel/film/cream/suppository). All patients (males and females of child-bearing potential\*) must also agree to use an acceptable method of contraception for 6 months following completion or discontinuation from the trial medication.

\*Women of childbearing potential are defined as:

- Any female who has experienced menarche and does not meet the criteria for "women not of childbearing potential" as described below

Women not of childbearing potential are defined as:

- Women who are postmenopausal (12 months with no menses without an alternative medical cause) or who are permanently sterilized (e.g., tubal occlusion, hysterectomy, bilateral oophorectomy or bilateral salpingectomy)

### **3.3.3 Exclusion criteria**

1. Patients who experienced Investigator-reported drug-related serious adverse events (SAEs) in Trial 1297.2.
2. ACR functional Class IV (see [Appendix 10.1](#)) or wheelchair/bed bound.
3. Primary or secondary immunodeficiency (history of, or currently active).
4. Positive QuantiFERON test.

5. Known clinically significant coronary artery disease or significant cardiac arrhythmias or severe congestive heart failure (New York Heart Association Classes III or IV), or interstitial lung disease observed on chest X-ray.
6. Anaphylactic reaction or hypersensitivity to adalimumab received in Trial 1297.2.
7. History or recent evidence of cancer including solid tumors, hematologic malignancies, and carcinoma in situ (except participants with previous resected and cured basal or squamous cell carcinoma, treated cervical dysplasia, or treated in situ Grade I cervical cancer within 5 years prior to the Screening Visit).
8. Positive serology for HBV or hepatitis C virus (HCV).
9. Patients who are expecting to receive any live virus or bacterial vaccinations during the trial, or up to 3 months after the last dose of trial drug.
10. Any treatment (including biologic therapies) that, in the opinion of the Investigator, may place the patient at unacceptable risk during the trial.
11. Patients with a significant disease other than RA and/or a significant uncontrolled disease (such as, but not limited to, nervous system, renal, hepatic, endocrine, or gastrointestinal disorders). A significant disease is defined as a disease which, in the opinion of the Investigator, may (i) put the patient at risk because of participation in the trial, or (ii) influence the results of the trial, or (iii) cause concern regarding the patient's ability to participate in the trial.
12. Premenopausal (last menstruation 1 year prior to screening), sexually active women who are pregnant or nursing, or are of child-bearing potential and not practicing an acceptable method of birth control, or do not plan to continue practicing an acceptable method of birth control throughout the trial (acceptable methods of birth control are intrauterine devices, surgical sterilization, double barrier, or vasectomized partner).
13. Current inflammatory joint disease other than RA (e.g., gout, reactive arthritis, psoriatic arthritis, seronegative spondyloarthropathy, Lyme disease) or other systemic autoimmune disorder (e.g., systemic lupus erythematosus, inflammatory bowel disease, pulmonary fibrosis, or Felty's syndrome, scleroderma, inflammatory myopathy, mixed connective tissue disease, or any overlap syndrome). Secondary Sjögren's syndrome or secondary limited cutaneous vasculitis with RA is permitted.
14. Any planned surgical procedure, including bone/joint surgery/synovectomy (including joint fusion or replacement) for the duration of the trial.
15. Known active infection of any kind (excluding fungal infections of nail beds), or any major episode of infection requiring hospitalization or treatment with intravenous (i.v.) anti-infectives within 4 weeks of the Screening Visit or completion of oral anti-infectives within 2 weeks of the Screening Visit.
16. Serious infection or opportunistic infection during the 1297.2 trial.
17. Any acquired neurological, vascular, systemic or demyelinating disorder that might affect any of the efficacy assessments, in particular, joint pain and swelling (e.g., Parkinson's disease, cerebral palsy, diabetic neuropathy) that occurred during the 1297.2 trial.
18. Currently active alcohol or drug abuse.

19. Treatment with i.v. Gamma Globulin or the ProSORBA® Column during the 1297.2 trial.
20. Planned treatment with i.v. intramuscular, intra-articular and parenteral corticosteroids.
21. Aspartate aminotransferase (AST) or alanine aminotransferase (ALT) >1.5 times upper limit of normal (ULN).
22. Hemoglobin <8.0 g/dL.
23. Platelets <100,000/ $\mu$ L.
24. Leukocyte count <4000/ $\mu$ L.
25. Creatinine clearance <60 mL/min.
26. Patients who are currently participating in another clinical trial other than Trial 1297.2.

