### 2.3 BENEFIT - RISK ASSESSMENT

Patient risk will be minimized in this trial by implementing conservative eligibility criteria. Due consideration has been given to previous experience with US-licensed Humira® and EU-approved Humira® in RA patients and side effect management advice (e.g., for hypersensitivity reactions) is provided for in this CTP. All trial personnel are directed to the BI 695501 IB for a description of the non-clinical and clinical experience with BI 695501. To date, a total of 175 healthy male volunteers (includes data from Trial 1297.8 and Trial 1297.1) have received BI 695501. As of 01 July 2015, 465 patients were included in Trial 1297.2.

Representatives from Boehringer Ingelheim (BI) and Safety, Clinical and Quality functions will review accumulating safety data at the monthly Medical and Quality Review Meeting.

Given the progressive nature of the disease, each patient will receive active RA treatment throughout the trial.

Patients will be carefully monitored during ambulatory (outpatient) visits for any safety signs and symptoms that may occur or arise following trial treatment. Adverse events (AEs), body temperature, vital signs, electrocardiograms (ECGs) and safety laboratory assessments as

well as immunogenicity data will be collected throughout the trial; therefore monitoring patients for safety outcomes over a prolonged period of time will be possible.

A potential for drug-induced liver injury (DILI, a rare event) is under constant surveillance by sponsors and regulators. Therefore, timely detection, evaluation, and follow-up of alterations of selected liver laboratory parameters to ensure patients' safety will be performed in this trial (see [Section 5.3.6](#)).

In addition, hypersensitivity reactions, anaphylaxis, and serious infections are considered adverse events of special interest (AESI), see Section 5.3.6.

In patients treated with Humira®, common adverse reactions reported in greater than 10% of patients include infections (e.g., upper respiratory tract infections, sinus infections), injection site reactions, headache and rash. Allergic reactions (e.g., allergic rash, anaphylactic reaction, fixed drug reaction, non-specified drug reaction, urticaria) have been observed in approximately 1% of patients ([R15-0739](#) and [R15-3225](#)).

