### **3.3.4 Removal of patients from therapy or assessments**

#### **3.3.4.1 Removal of individual patients**

Patients who do not meet all of the inclusion criteria or who meet one or more of the exclusion criteria will not be enrolled in this extension trial. The primary reason for the screen failure will be recorded on the electronic Case Report Form (eCRF).

Patients have the right to withdraw from this trial at any time for any reason.

Two situations can occur in this trial and need to be documented accordingly, as follows:

1. An individual patient is to be withdrawn from the trial if:
  - The patient decides to discontinue participation in the trial by withdrawal of consent. In this case, no more investigations will be performed. The patient does not have to justify the decision.
2. Based on assessment by the Investigator, and after consultation with the trial medical advisor, an individual patient may be discontinued from treatment with the investigational compound if:
  - The patient needs to take concomitant drugs that interfere with the investigational product or other trial medication
  - The patient can no longer be treated with trial medication for other medical reasons (such as surgery, adverse or drug-related events, other diseases, or pregnancy)
  - Repeated protocol violation after documented discussion with the medical monitor
  - Lack of efficacy
  - The patient has an AE that is categorized as a serious infection. A serious infection is defined as infections requiring i.v. antibiotics or those that meet the regulatory definition of a SAE (including, but not limited to, systemic fungal infections, human immunodeficiency virus [HIV], HBV, HCV, infected joint prosthesis)
  - Patient lost to follow-up despite reasonable efforts to make contact with the patient

If a patient permanently discontinues trial medication for any reason, every effort should be made for the patient to attend the EoT Visit as soon after trial treatment discontinuation as possible. Every effort should be made for all patients who discontinue the trial treatment early, to return for a safety follow-up visit 10 weeks after the last dose of trial medication. For details of assessments to be performed at the Week 48 visit and the Week 58 visit, see [Sections 6.2.2](#) and [6.2.3](#), respectively.

For all patients the reason for withdrawal (e.g., AEs) must be recorded in the eCRF. These data will be included in the trial database and reported.

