## 6.2 DETAILS OF TRIAL PROCEDURES AT SELECTED VISITS

### 6.2.1 Screening period

#### Screening Period (Day -14)

Once the patient has provided informed consent (before any 1297.2 or 1297.3 trial-specific procedures or assessments are performed) and meets all inclusion criteria and none of the exclusion criteria (see [Section 3.3](#)), the trial site will enter the screened patient into the system using the Interactive Response Technology (IRT).

The following will also be performed/collected:

- Demographic information (including gender, date of birth, ethnicity and race), and medical and surgical history (including RA history and history of opportunistic infection)
- Evaluation of patient's willingness and ability to self-administer trial medication
- Physical examination, including height (cm) and weight (kg) (see [Section 5.3.1](#))
- Infection screen (HBsAg, HCV and HIV test, per the Investigator's discretion)
- Urine pregnancy test for women of child-bearing potential
- Patient questionnaires: global VAS, HAQ-DI and SF-36 v2 (see [Section 5.2](#))
- Joint assessment (see Section 5.2)
- TB test (QuantiFERON®-TB Gold test)
- ESR and CRP
- Physician questionnaire: global VAS (see Section 5.2)
- Vital signs (blood pressure, pulse rate, respiratory rate, and body temperature; see [Section 5.3.2](#))
- Laboratory testing (serum chemistry, hematology and urinalysis; see [Section 5.3.3](#))
- 12-lead ECG (see [Section 5.3.4](#))
- Previous and concomitant therapy (see [Section 4.2](#))
- Assessment of AEs (see [Section 5.3.6](#))

Once patients have signed the ICF, completed screening, and eligibility is confirmed, the Investigator will contact IRT and patients will be assigned to treatment with BI 695501. As part of the Trial 1297.2 Week 48 assessments, trial medication is administered. This is the last trial medication administration of the 1297.2 trial. During this visit, the Investigator/designee will train the patient on how to self-administer the trial medication. See [Section 4.1.4](#) for details.

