## 9. DISPOSITION AND WITHDRAWALS

All subjects who provide informed consent will be accounted for in this trial.

The counts of the analysis sets will be presented:

- All Subject Enrolled (ENR)
- All Subjects Assigned (ASD)
- Safety Analysis Set (SAF)
- Full Analysis Set (FAS)
- Pharmacokinetic Full Analysis Set (PKFS)

The following subject disposition and withdrawals will be presented for the ENR set:

- Screened
- Screen failure (defined as subjects who do not enter the trial and are not assigned treatment), reason for non-inclusion
- Assigned to treatment
- Assigned to treatment but not treated
- Treated
- Completed treatment

---

Document: \\jeedc-nas01a\BIOSdata\Boehringer\_Ingelheim\BI\_695501\NVA96235\Biostatistics\Documentation\SAP\10  
v1.0\BI\_1297.3\_SAP\_22JUN2016\_v1.0

Author: Version Number: 1.0  
Version Date: 22JUN2016

Template No: CS\_TP\_BS016 – Revision 3  
Effective Date: 01May2012

Reference: CS\_WI\_BS005

- Completed trial
- Discontinued from treatment, reason for premature discontinuation from treatment
- Discontinued from trial, reason for premature discontinuation from trial
- Discontinued from safety follow-up, reason for premature discontinuation from safety follow-up

Subjects enrolment will also be summarized by country and by age group (18-64, 65-84, >=85).

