## 9.1. IMPORTANT PROTOCOL DEVIATIONS

Important protocol violations defined below will be listed for the ASD set:

- Trial drug not administered at all
- Severe violation of treatment compliance
  - Medical team will review subjects with treatment compliance outside 80% and 120% (refer to section 14.1) and decide if the violation is severe.
- Any deviation of inclusion/exclusion criteria should be considered as important violations.
- A severe violation to the restricted DMARD therapy (protocol table 4.2.2.1:1), as assessed by the medical team.

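### Inclusion 4 accepts birth control pills but exclusion 12 leaves them out, and exclusion 12 bars nursing women only if they are sexually active

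*Protocol*

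**What the plan says.** Inclusion criterion 4 (protocol Section 3.3.2) requires reliable contraception from participants of either sex who have reproductive potential. It lists the options as follows: "Acceptable methods of birth control include, for example, birth control pills, intrauterine devices, surgical sterilization, vasectomized partner and double barrier method".

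Exclusion criterion 12 (Section 3.3.3) returns to the subject for premenopausal, sexually active women. It excludes those of child-bearing potential who do not use, or do not plan to keep using, an acceptable method, and it defines the term: "acceptable methods of birth control are intrauterine devices, surgical sterilization, double barrier, or vasectomized partner". The same sentence carries the pregnancy and nursing exclusion, which covers "sexually active women who are pregnant or nursing".

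Section 3.3.4.1 gives the enrolment rule: patients "who meet one or more of the exclusion criteria will not be enrolled in this extension trial". Section 2.3 states the general intention: "Patient risk will be minimized in this trial by implementing conservative eligibility criteria".

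In the SAP, Section 9 will report "Screen failure (defined as subjects who do not enter the trial and are not assigned treatment), reason for non-inclusion". Section 9.1 says: "Any deviation of inclusion/exclusion criteria should be considered as important violations". Section 5.4 defines no per-protocol set.

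**The concern.** Each patient should get one answer from the eligibility text. Here a woman whose only contraception is the pill is told by one criterion that her method is acceptable and is barred for it by another. Sites that work from different criteria would handle the same patient differently, and about 80 sites are planned.

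The second problem is one of safety wording. Whether a woman is sexually active matters to a contraception rule. The protocol gives no reason why it should matter to a nursing exclusion, yet the sentence structure makes the exclusion depend on it.

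**Working it through.** No figure in the plan is at issue, so the check is a comparison of texts.

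**Contraception lists**

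| Method | Inclusion 4 | Exclusion 12 |
|---|---|---|
| Birth control pills | named | absent |
| Intrauterine device | named | named |
| Surgical sterilization | named | named |
| Vasectomized partner | named | named |
| Double barrier | named | named |
| Form of list | illustrative | closed |

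Inclusion 4 names 5 methods and exclusion 12 names 4. All 4 are shared, so 5 − 4 = 1 method, the pill, appears in inclusion 4 only.

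Timing does not separate the two rules, since both run for the whole of trial participation. Take a premenopausal, sexually active woman of child-bearing potential who uses only the pill:

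1. Inclusion 4: met, because her method is named.
2. Exclusion 12: met, because her method is not on the closed list.
3. Section 3.3.4.1: meeting one exclusion bars enrolment, so on a literal reading she is not enrolled.

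A site that follows exclusion 12 records a screen failure with a reason (SAP Section 9). A site that follows inclusion 4 enrols her, and by SAP Section 9.1 that enrolment is an important violation. I found nothing in the protocol, its amendment description or the SAP that reconciles the lists.

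**Nursing**

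Take a nursing woman who is not sexually active:

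1. Exclusion 12: not met, because the qualifier fails.
2. Other criteria: none names nursing in the text provided. Exclusions 10 and 11 concern risky treatments and significant disease.
3. What remains is the Investigator's general judgement of benefit under inclusion 2.

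Pregnancy shares the flawed wording but has practical safeguards. The Screening list in Section 6.2.1 includes "Urine pregnancy test for women of child-bearing potential", and the Day 1 list in Section 6.2.2 repeats it. That makes 2 scheduled pregnancy tests up to and including the first-dose visit. Checks of nursing status listed at those two visits: 0.

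**The case against.** The strongest reply has four parts.

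- **The outcome for pill users is settled.** Criteria are cumulative, so the stricter one governs and no safety is lost. This is right about the literal outcome. It does not remove the contradiction, because the text does not show which rule the sponsor meant.
- **The lists differ in scope.** Inclusion 4 covers both sexes and gives examples, while exclusion 12 covers a subset of women. A general list followed by a narrower rule is a possible reading. However, inclusion 4 does not divide its list by sex, and the pill is a method that only women take. It is also fair to say that one in five counts items in an open list; it is not a rate of anything.
- **The violation may never be listed.** A site that accepts the pill under inclusion 4 may see no deviation to record, and the documents describe no check aimed at finding one. This stands: the SAP classifies the deviation but does not guarantee that it is detected.
- **The nursing case is remote.** Entrants come straight from 48 weeks of treatment in Trial 1297.2 and must stay on methotrexate to Week 12. Medical history, exclusion 10 and the product reference documents also leave room for judgement. The rarity stands. The rest is discretion or reference material and does not amount to a nursing exclusion. Consent pages are not in the copy reviewed, so the absence is established only for the text available.

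**Conclusion.** Both parts hold. Exclusion 12 contradicts inclusion 4 on one method, the pill, and its nursing exclusion does not cover a woman who is not sexually active. These are operative rules that are wrong as written, though the correction is small.

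The number of patients affected cannot be given. The documents contain no figures for child-bearing potential, pill use or nursing. They also do not contain Trial 1297.2's contraception rules, which decide whether any entrant relies on the pill alone. The effect on planned estimates is nil: the protocol plans descriptive analyses only, and without a per-protocol set an eligibility deviation removes nobody from an analysis set. What changes is who may be enrolled, how screening failures and deviations are recorded, and whether the nursing exclusion protects every nursing woman.

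**What to change.** State the acceptable methods once, in inclusion 4, and have exclusion 12 refer to that list. The sponsor should decide whether pills are acceptable: if so, they stay in inclusion 4; if the stricter rule is intended, delete them there. Separately, make being pregnant or nursing an exclusion of its own, with no condition on sexual activity or menopausal status.

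The cost is a few lines in Sections 3.3.2 and 3.3.3, carried in the next amendment. No new procedure is needed and no analysis changes.
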